12.3 Planned Interim Analyses

Interim Analyses: A masked interim analysis of the primary study outcome will be performed after approximately half of the sample has completed the 6-month examination. A Lan-Demets spending function with an O'Brien-Fleming type boundary will be used, with p-values for efficacy at 0.000001709 and 0.00099938 at 50% and 100% completion, respectively. Non-binding p-values for stopping due to futility at 50% and 100% completion will be 0.2336928 and 0.00099938, respectively.

12.3.1 Safety & Efficacy Review

Safety-related stopping rules for the trial as outlined in [Section 9.5](#) would occur due to participant safety concerns.

The trial may be terminated for early efficacy or futility based on the results of an interim analysis, as described in the Statistical Analysis Plan. The interim analysis will be conducted after approximately half of the participants have completed the 6-month examination.

The DSMB, NIDCR, and IRBs would be consulted regarding stopping the trial.

12.4 Final Analysis Plan

We will consider all relevant biological variables (e.g., gender, race/ethnicity, and age) in the analyses. The initial analyses will involve exploration of the data. Continuous variables may be transformed or categorized based on the observed distribution. Categorical variable response categories may be collapsed due to small sample sizes. Whether race and ethnicity are analyzed separately or as a single variable depends upon whether the Hispanics in the trial are primarily White or if they also include Black Hispanics. Because randomization is stratified by trial site, trial site will be included as a covariate in all analyses.

Aim 1 (Cavitated caries lesion arrest at 6 months follow-up): The proportion of arrested cavities at the 6-month visit will be compared between the SDF and placebo-treated groups first using a generalized estimating equation (GEE) model for binary outcomes, using an exchangeable correlation to account for possible non-independence among multiple cavities within a participant. Trial site will be included as a covariate.

Secondary analyses of the proportion of arrested lesions will extend the GEE model for binary outcomes to include covariates and their interactions with the treatment effect; covariates will include race/ethnicity, gender, age, trial site, initial ICDAS score, tooth location (anterior/posterior; as there are some data in the literature to suggest a difference in SDF efficacy) and number of affected teeth. Interactions of the

covariates with treatment will be explored to examine the results for differential treatment effects. However, the analyses are not specifically powered to detect these interactions.

Note: As this trial may enroll siblings, at the time of analyses we intend to explore the correlations within participants and correlations between siblings to aid in determining the appropriate modeling technique to use. As described above the current analysis plan uses GEE models to account for correlations among multiple cavities within a participant. The GEEs could be extended to account for siblings by correlating all cavities within a family, rather than within a participant. However, this assumes the same within family correlation. An alternative approach is to account for the two levels of correlations (cavities within participants, participants within families) by switching the analyses to use generalized linear mixed models (GLMM) instead of GEE. One difficulty we anticipate with a switch to GLMM is estimation of the random effects – the number of families with enrolled siblings may not be large enough to properly estimate the two random effects within the GLMMs.

Aim 2 (Cavitated caries lesion arrest at 8 months follow-up): The same GEE model for binary outcomes as used for Aim 1 will be used to compare the proportion of arrested lesions at approximately 8-months to examine Aim 2.

Sub-Aim 2a (Compare the effect of one application of 38% SDF at 3 and 6 months follow-up on caries lesion arrest): A longitudinal (repeated measures) model for binary data that incorporates both the correlation within each subject at each time and across the time points will be used to compare the proportion of arrested caries lesions at approximately 3 and 6 months. Trial site will be included as a covariate.

Aim 3 and Sub-Aim 3a (pain): At the 3-, 6-, and 8-month visits, the proportion of participants who have experienced pain with treated teeth during the follow-up period will be compared between the SDF and placebo-treated groups using Cochran-Mantel-Haenszel chi-square tests, with trial sites as the strata.

The total number of episodes of pain associated with trial teeth per participant (calculated by adding all reports of pain throughout the trial verified by a clinical exam to be associated with a trial tooth) during the follow-up period will be compared between the SDF and placebo treated groups using generalized linear models (GLMs) for count data, with trial site included as a covariate. The DDQ score will be compared between groups using analysis of covariance at each follow-up visit, with trial site included as a covariate.

Additional GLMs for binary and count outcomes and analysis of covariance models for continuous outcomes, as appropriate for each outcome above, will analyze the effects of covariates and their interactions with the treatment effect.

Aim 4 (Family-level outcomes): The P-CPQ, FIS, and satisfaction and acceptability scores will be compared between the SDF and placebo-treated groups using analysis of covariance, with trial site included as a covariate.

Additional analyses will consider the effects of covariates and their interactions with the treatment effect.

Changes in the color of treated lesions over time will be compared between treatments using a Cochran-Mantel-Haenszel chi-square test, with trial sites as the strata.

The family's experiences with ECC, child's brushing and dietary habits, and color change will be examined as additional covariates for the analyses of satisfaction and acceptability scores.

Safety: The proportion of infected trial teeth at each visit will be compared between the SDF and placebo-treated groups using a generalized estimating equation (GEE) model for binary outcomes, using an exchangeable correlation to account for possible non-independence among multiple teeth within a participant. Trial site will be included as a covariate.

The proportion of participants with adverse events (gum infection, oral mucositis, allergic reaction, anaphylaxis, nausea, vomiting, gastrointestinal pain, diarrhea; individually and the presence of any of the events) during the follow-up period will be compared between the SDF and placebo-treated groups using Cochran-Mantel-Haenszel chi-square tests, with trial sites as the strata.

12.4.1 Analysis populations

The primary analysis will be conducted using the intent-to-treat (ITT) population. The ITT population will include all randomized subjects. Analyses will also be performed using the per-protocol (PP) population. The PP population will be limited to subjects who complete all dental examinations and surveys/questionnaires for the baseline, 3-month, 6-month, and 8-month visits within the specified study windows and complete the intermediate contacts at 1.5, 4.5, and 7 months within the specified study windows.

12.4.2 Missing data

As noted in [Section 5.5](#), any lesions removed from the trial due to the “early exit strategy” will be considered to be treatment failures – non-arrest of the lesion and presence of pain and/or infection requiring removal of the tooth from the study – and not considered to be missing data.

The primary method for handling missing data will be to use a multiple imputation analysis, with imputations based on race/ethnicity, gender, age, trial site, initial ICDAS score, tooth location, treatment, and most recent prior visit results will be performed. Twenty-five imputed datasets will be created, and results will be combined using standard methods.

A sensitivity / tipping point analysis will also be performed to evaluate the MAR (missing at random) assumption for the missing primary efficacy outcome (caries arrest at approximately 6 months). A pattern-mixture approach to the missing data imputation (missing not at random, MNAR) will be applied to the logistic regression model used for imputing the missing caries arrest at approximately 6 months outcome from the variables described above. To represent MNAR, a range of shift parameters will be used to adjust the log odds ratios for the SDF-treated group. The tipping point will be identified as the amount of shift needed to change the statistical significance of the treatment comparison using the primary efficacy analysis. The size of the shift required to change the statistical significance will be used to gauge the plausibility of the MAR assumption.

13 SOURCE DOCUMENTS AND ACCESS TO SOURCE DATA/DOCUMENTS

Data will be collected on a combination of paper source documents and on electronic Case Report Forms (eCRF). When data is directly entered into the clinical database the eCRF will serve as the source document. Data will include ICDAS examination data, safety data, and parent/guardian survey responses to address tertiary objectives. A commercially-developed, FDA-compliant, web-based electronic data capture system will be utilized for this trial.

Trial staff will maintain appropriate medical and research records for this trial, in compliance with ICH E6, Section 4.9 and regulatory and institutional requirements for the protection of confidentiality of participants. Trial staff will permit authorized representatives of NIDCR and regulatory agencies to examine (and when required by applicable law, to copy) research records for the purposes of quality assurance reviews, audits, and evaluation of the trial safety, progress and data validity.

14 QUALITY CONTROL AND QUALITY ASSURANCE

Each clinical site is responsible for maintaining quality control at their site. This includes managing the security, integrity and completeness of items such as Case Report Forms, consents, and medical histories. Any data stored electronically must be handled in accordance with federal institutional policies. The Project Manager will provide oversight of Quality Management (QM). The Project Manager will work with the sites (recruitment centers) to develop plans for appropriate internal quality management that incorporate elements of quality control and quality assurance. These quality management plans will provide site staff with the means to identify and resolve problems with protocol implementation and regulatory compliance.

To ensure consistency in ICDAS examinations across different examiners and trial sites, an examiner calibration session will occur prior to trial initiation. All dental examiners will be trained and calibrated in the use of the ICDAS II criteria for dental caries, including assessment of dentin hardness and color in cavitated lesions. Examiners will also be trained in the management and examination of young children.

The recruitment centers should follow their institutional SOPs, where relevant, to conduct the trial per protocol for Quality Assurance. The SOPs should be available to the trial monitor during monitoring visits.

14.1 Participant Binder

All essential trial documents must be retained by the investigator in a Participant Binder and generally include the following:

- Source documents
- Paper questionnaires completed by the participant
- Paper CRFs
- Data correction forms

14.2 Regulatory Binder

All essential regulatory documents must be maintained by the investigator. These generally include the following:

- IRB documents, including approved consent(s)
- Investigator and Sub-Investigator CVs or documentation of qualifications and training
- Delegation of Responsibility Log, and
- Monitoring Reports

15 ETHICS/PROTECTION OF HUMAN SUBJECTS

15.1 Ethical Standard

The investigator will ensure that this trial is conducted in full conformity with the principles set forth in The Belmont Report: Ethical Principles and Guidelines for the Protection of Human Subjects of Research, as drafted by the US National Commission for the Protection of Human Subjects of Biomedical and Behavioral Research (April 18, 1979) and codified in 45 CFR Part 46 and/or the ICH E6.

15.2 Institutional Review Board

The protocol, informed consent form(s), recruitment materials, and all participant facing materials will be submitted to the single IRB (sIRB) of record for review and approval. Additionally, all trial sites will submit institutional IRB submissions to cede to a single IRB.

Approval of both the protocol and the consent form must be obtained before any participant is enrolled. Any amendment to the protocol will require review and approval by the IRB before the changes are implemented in the trial.

15.3 Informed Consent Process

A waiver of informed consent and HIPAA will be requested to access potential child participant names, telephone numbers, addresses, and dental records to pre-screen for eligibility. This information will be used to introduce the trial to parents/legal guardians of children who may be eligible to participate. If the parent/guardian is interested, her/his consent will be obtained. See below for more detail on these processes.

Parents/legal guardians of children with potentially eligible lesions will be informed about the trial, and if interested will undergo the consenting process. If pre-screening happens during the school day, when parents/guardians are not present, the pre-screening results and information about the trial, and invitation to schedule a baseline visit, will be sent home with the child. Interested families will call the trial team or will receive a call from the trial team and will undergo review of the inclusion/exclusion criteria over the phone, and receive a brief explanation of the trial. If they agree to participate, the consenting process will occur.

Participant Consent: The consent forms will be reviewed and informed consent will be obtained prior to any trial activities. The parent/guardian must consent for the child and her/himself. Participants will be given a copy of the signed consent form.

How it will be determined whether the participants understand the information that was provided in the consent document: We will determine whether the participants understand the information that is provided in the consent document by reviewing it in detail with the participant, answering any and all questions the participant may have, and asking the participant to explain the trial back to the person obtaining consent. Participants will be asked to reiterate in their own words what they will need to do as participants in the trial and what the potential risks and benefits are. If participants do not ask any questions about the document, but appear confused or unclear about what was explained to them, then the person obtaining consent will attempt to identify the area(s) of uncertainty and clarify the content for the research participant.

For participants who may prefer the use of other languages, trial materials will be translated by a translator into selected languages, and available translated versions of the consent will be used. In addition, trial personnel fluent in selected languages will be available at sites if needed.

A record of consented participants will be kept in the regulatory binder. The Data and Clinical Coordinating Center (DCCC) will also keep a record of trial ID of those who provided consent.

15.4 Exclusion of Women, Minorities, and Children (Special Populations)

Include	Exclude	Vulnerable Population Type
	X	Adults unable to consent
X		Individuals who are not yet adults (e.g., infants, children, emancipated minors)
	X	Wards of the State (e.g., foster children)
X		Pregnant women
	X	Prisoners

Inclusion of Women

No potential participants will be excluded from participation based on their gender. It is anticipated that a roughly equal number of boys and girls ages 12 to 71 months will be included in this trial. It is also anticipated, based on our other studies that the person identified and recruited as the parent/legal guardian in most cases will be the mother.

Inclusion of Minorities

The aim of this trial is to decrease disparities in young, diverse (ethnicity, race, location-urban, rural) U.S. children with high risk for dental caries, by conducting a multi-site longitudinal prospective trial. Thus, inclusion of minorities is crucial to this project's aim. Ethnicity and race of the caregiver and child will be identified by the caregiver.

15.5 Participant Confidentiality

Participant confidentiality is strictly held in trust by the investigators, trial staff, and the sponsor(s) and their agents.

The trial protocol, documentation, data, and all other information generated will be held in strict confidence. No information concerning the trial or the data will be released to any unauthorized third party without prior written approval of the sponsor.

The trial monitor or other authorized representatives of the sponsor may inspect all trial documents and records required to be maintained by the investigator. The clinical trial site will permit access to such records.

Any data, forms, reports, and other records that leave the university that collected the data will be de-identified of any protected health information (PHI) and replaced with trial identifier to maintain participant confidentiality. However, as many trial visits will occur off-site (e.g., head start centers, other dental clinics, etc.), trial teams will need to carry parent/legal guardian and child names with them at those times to identify the child's PIN for data collection. Information will not be released without written permission of the participant, except as necessary for: monitoring by the IRB, OHRP, NIH or its designee and/or any other government officials; and safety monitors/committees that may need the information to make sure that the trial is done in a safe and proper manner, and/or analyze the results of the trial.

To further protect the privacy of trial participants, the Secretary, Health and Human Services (HHS), has issued a Certificate of Confidentiality (CoC) to all researchers engaged in biomedical, behavioral, clinical or other human subjects research funded wholly or in part by the federal government. Recipients of NIH-funded human subjects research are required to protect identifiable research information from forced disclosure per the terms of the NIH Policy (see <https://humansubjects.nih.gov/coc/index>). As set forth in *45 CFR Part 75.303(a)* and *NIHGPS Chapter 8.3*, recipients conducting NIH-supported research covered by this Policy are required to establish and maintain effective internal controls (e.g., policies and procedures) that provide reasonable assurance that the award is managed in compliance with Federal statutes, regulations, and the terms and conditions of award. It is the NIH policy that investigators and others who have access to research records will not disclose identifying information except when the participant consents or in certain instances when federal, state, or local law or regulation requires disclosure. NIH expects investigators to inform research participants of the protections and the limits to protections provided by a Certificate issued by this Policy.

15.6 Future Use of Stored Specimens and Other Identifiable Data

The informed consent document will request permission from the parent/legal guardian to contact him/her for potential future studies. The parent/legal guardian will either consent to allow contact from the trial team to assess interest in potential future studies or will decline.

16 DATA HANDLING AND RECORD KEEPING

The investigators are responsible for ensuring the accuracy, completeness, legibility, and timeliness of the data reported. All source documents should be completed in a neat, legible manner to ensure accurate interpretation of data. The investigators will maintain adequate case histories of trial participants, including accurate case report forms (CRFs), and source documentation.

16.1 Data Management Responsibilities

The University of Michigan in collaboration with Rho, Inc. will serve as the Data and Clinical Coordinating Center (DCCC) for this trial. Data collection and accurate documentation are the responsibility of the trial staff under the supervision of the investigator, lead site coordinator, and project manager. All source documents must be reviewed by the trial team and data entry staff, which will ensure that they are accurate and complete. Unanticipated problems and adverse events must be reviewed by the investigator or designee in a timely manner (please see the MOP for more details).

16.2 Data Capture Methods

Data will be captured via paper source documents or directly entered into the electronic database, with the eCRF serving as the source document for directly entered data.

16.3 Types of Data

The material collected from participants will include data from clinical exams and trial questionnaires, specifically:

- Data collected during the trial pre-screening visit (recruitment) will include eligibility criteria, demographics such as sex, race/ethnicity, age, etc.
- At baseline/24-48 hour contacts/visits, and the 3-month, 6-month, and 8-month clinical trial visits, trial questionnaires including, for example dental discomfort (Appendix B), oral health-related quality of life (Appendix C), and family survey (Appendix D) will be collected. An oral soft tissue exam will be completed. A medical history will be collected at baseline and re-assessed at approximately 6 months or between 4.5 month and 6 month visits. The ICDAS examination of the oral cavity will include scoring of teeth present and absent, as well as presence of caries lesion severity and activity (Appendix A). Cavitated lesions' data for ICDAS score of 5 or 6 will further include hardness and color. For SDF/placebo application (during baseline and 6 month visits), time of application will be recorded.
- Data regarding Adverse and Serious Adverse Events as well as Unanticipated Problems will be collected and reported as needed throughout the trial.
- During the 1.5-, 4.5-, and 7-month Intermediate Contacts, contact information will be updated. Additionally, brief questions inquiring about side effects of the SDF/placebo treatment will be asked, in addition to administration of the dental discomfort questionnaire (Appendix B) to determine if an unscheduled clinic visit is necessary to evaluate the child. Contact information will also be updated during the in person 3- and 6-month trial visits.

16.4 Schedule and Content of Reports

Enrollment and retention data will be reviewed on a regular basis by the Executive Committee and NIDCR. The Executive Committee will be led by the trial PI, and will include the Project and Data Manager, the site PIs, the site lead coordinators, the trial biostatisticians, the NIDCR representatives, and Rho representatives. The Committee will review AEs/SAEs/UPs, reports to the Data and Safety Monitoring Board (DSMB), and interim analysis upon conclusion of the 6-month visits for approximately 50% of the total sample.

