5.4 Treatment Assignment Procedures

Randomization will be stratified by site. Allocation to SDF/placebo will be 1:1.

5.4.1 *Randomization Procedures*

The randomization schedule will be generated by a biostatistician. Biostatisticians who will be involved in the analyses will remain masked to the trial randomization.

Randomization procedures are explained in more detail in the MOP and the Randomization Plan.

5.4.2 *Masking Procedures*

To ensure concealment of treatment allocation, the identical ampules containing test and placebo product will be assigned sequential identification numbers. The master randomization schedule will not be broken until analyses of the data, or if requested by the DSMB for meetings or due to safety concerns. All trial product will be sealed and labeled as required by the FDA [Section 6.0].

The following steps are being taken to minimize issues associated with bias and masking: 1) Product will be concealed in identical unit-dose ampules, identified by identification numbers, and with liquids of equal color. 2) The trial personnel applying the concealed product at baseline and 6 months will be separate from the trial ICDAS examiner. 3) The parent/guardian, child, and trial caries examiners and trial team involved in any data collection will remain masked regarding trial group allocation. 4) The primary trial outcome (hardness) will be measured independently of the outcome of color (to acknowledge teeth can turn dark, and still remain soft) for all cavitated caries lesions (not only those included and treated in the trial).

5.4.3 *Breaking the Blind*

Randomization code assignment will be broken only under circumstances where participant safety is in question. The participant will be withdrawn from the trial upon breaking of the randomization assignment.

Unmasking of individual subjects' treatment assignments should occur only when knowledge will have a direct bearing on the medical treatment or evaluation of a subject. Whenever possible, the need to unmask should be discussed with the Grant PI and the NIDCR Medical Monitor prior to unmasking. Unmasking procedures are described in more detail in the MOP.

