7. DATA SAFETY MONITORING BOARD

In addition to the PI's responsibility for oversight, trial oversight will be under the direction of a Data and Safety Monitoring Board (DSMB) composed of members with appropriate expertise in pediatric dentistry, pediatrics, statistics, ethics, and other scientific disciplines. Members will be appointed by NIDCR. The DSMB will meet at least annually to assess safety and efficacy data, trial progress, and data integrity for the trial. If safety or data integrity concerns arise, more frequent meetings may be held. The DSMB will operate under the rules of an NIDCR-approved charter that will be approved at the organizational meeting of the DSMB. The DSMB will provide recommendations to the NIDCR.

In order to maintain clinical trial integrity, there will be firewalls in place to ensure the interim analysis results will be limited to only those related experts (e.g., unmasked DSMB members, unmasked independent biostatistician) who are independent of the personnel involved in conducting and managing this study.

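### Protocol 16.4 has the Executive Committee review the interim analysis, while SAP 7 limits interim results to people independent of trial conduct; the two must be reconciled and the committee's access defined

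*Protocol*

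**What the plan says.** Protocol 16.4 defines the committee's membership: "The Executive Committee will be led by the trial PI, and will include the Project and Data Manager, the site PIs", followed by "the site lead coordinators, the trial biostatisticians, the NIDCR representatives, and Rho representatives". Its duties follow: "The Committee will review AEs/SAEs/UPs, reports to the Data and Safety Monitoring Board (DSMB), and interim analysis upon conclusion of the 6-month visits", timed at about half of the total sample.

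Protocol 12.3 describes the analysis in question: "A masked interim analysis of the primary study outcome will be performed after approximately half of the sample has completed the 6-month examination". Protocol 12.3.1 gives its purpose: "The trial may be terminated for early efficacy or futility based on the results of an interim analysis".

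SAP 7 promises "firewalls in place to ensure the interim analysis results will be limited to only those related experts". Its examples are unmasked DSMB members and an unmasked independent biostatistician, and it requires recipients "who are independent of the personnel involved in conducting and managing this study".

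On statisticians, Protocol 5.4.1 says: "Biostatisticians who will be involved in the analyses will remain masked to the trial randomization". SAP 5 keeps the Project Biostatistician masked until after database lock. SAP 9, which lists changes from the protocol's analyses, says nothing about who may see the interim.

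**The concern.** A firewall around interim efficacy results keeps the people who recruit, retain and manage participants from acting on the emerging effect. The people whom 16.4 names as reviewers are the people whom SAP 7 shuts out, so both rules cannot be followed.

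This trial has some features that make early knowledge of the effect unwelcome:

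- The primary outcome is a tactile judgement of dentin hardness, with an instruction in Protocol Appendix A on how to score when in doubt.
- Site investigators have discretion over eligibility on grounds of compliance (Protocol 5.2), and an investigator may end a child's participation (5.5.1).
- Teeth exited early count as failures (Protocol 7.3.3, SAP 6.11.1).

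There is also a second route. The committee reviews reports to the DSMB, and Protocol 10 says the DSMB assesses efficacy as well as safety data at least annually. Protocol 16.4 does not separate pooled reports from reports by arm.

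**Working it through.** The point concerns access to results and does not depend on arithmetic. The arithmetic only establishes what kind of result is at issue.

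1. **What the interim is.** Inputs: overall two-sided alpha 0.001 (SAP 6.1); Lan-DeMets spending of O'Brien-Fleming type at information 0.5 (SAP 8). Alpha spent per side = 2 × [1 − Φ(z(1 − 0.0005/2)/√0.5)] = 2 × [1 − Φ(3.481/0.7071)] = 8.543 × 10⁻⁷. Doubled for two sides, this is 0.0000017086, against 0.000001709 stated. The final boundary, with correlation √0.5 between looks, is z = 3.2907, or p = 0.00099936, against 0.00099938 stated. The plan's thresholds are reproduced, so the interim is a formal between-arm test of the primary outcome.

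2. **What its result would convey.** Planning assumptions (SAP 4): 3 lesions per child, within-child correlation 0.5, arrest near 50%. Design effect = 1 + (3 − 1) × 0.5 = 2. At 572 children, lesions per arm = 3 × 286 = 858. Standard error of the difference = √(2 × 0.25 × 2/858) = 0.034. The interim boundary is z = 4.785, so crossing it takes an observed difference of about 4.785 × 0.034 = 0.163, or 16 percentage points. A report labelled A and B would still show the size of the difference, with a standard error of about 3.4 points. Coding hides only the direction. A reader could presume that, since Protocol 2.2 cites 72% against 5% arrest in a short-term placebo-controlled trial.

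3. **Who is on each list.** Protocol 16.4: trial PI, project and data manager, site PIs, site lead coordinators, trial biostatisticians, NIDCR and Rho representatives. SAP 7: only experts independent of trial conduct and management. At least the trial PI, site PIs, site lead coordinators and data manager fall on the wrong side of the SAP 7 line.

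4. **Whether anything reconciles them.** Protocol 12.3 calls the interim masked but does not say what the committee is shown. Protocol 5.4.2 protects the randomization schedule, not aggregate results. Protocol 12.3.1 refers to the SAP for interim-based termination, and SAP 8 gives boundaries but no recipients. SAP 9 is silent. No section limits the committee to pooled data or to the DSMB's recommendation.

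5. **How many children could be affected.** The interim comes at about half the sample, leaving 1144 − 572 = 572 for later 6-month examination. This is a ceiling. Enrolment runs over about 4 years, so more children would be examined between the data cut and any committee meeting. If the 10% attrition anticipated in Protocol 12.2 is taken off the 572, about 515 remain. Some children already seen at 6 months would still owe the 8-month examination, a key secondary endpoint; their number is not given.

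**The case against.** The strongest reply is that the safeguard already exists. SAP 7 is explicit and specific, while the clause in 16.4 is one phrase in a general section on reporting. Reviewing the interim analysis could mean seeing a pooled report or hearing the DSMB's recommendation. The DSMB charter and the Manual of Procedures, which are not among the documents at hand, may settle access. All of this stands as a reason not to assume exposure. It does not remove the contradiction: 16.4 names the interim analysis itself, without limit.

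Four stronger readings are tempting and not supported:

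- **That site leaders saw, or certainly would see, efficacy by arm.** No section describes such a display.
- **That hardness scoring would be biased.** Caries examiners do the scoring. They are not named as committee members, and nothing says that site PIs or coordinators score lesions. Protocol 5.4.2 separates the person applying the product from the examiner and has hardness measured independently of colour. Protocol 2.3.1 notes that placebo lesions may also discolour. The remaining paths, through recruitment, retention and investigator discretion, are plausible but unquantified.
- **That the masked statisticians would be unmasked.** Protocol 5.4.1 and SAP 5 mask them to randomization, and a coded or pooled report does not reveal it. Their presence on the committee weakens the separation in SAP 7 but does not by itself breach 5.4.1.
- **That the protocol outranks the SAP.** The documents do not say which prevails here. The protocol's Supplemental Materials page places the SAP outside the protocol, while Protocol 12 and 12.3.1 defer statistical detail and interim termination to it.

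**Conclusion.** The inconsistency is real and plain on the page: Protocol 16.4 and SAP 7 give incompatible rules on who reviews the interim analysis. As written, 16.4 permits, but does not prove, exposure of trial leadership to interim results on the primary outcome, even with coded arms. The ceiling is about 572 of 1144 children still to be examined at 6 months. That assumes the committee meets at the data cut, no further examinations occur in between, there is no attrition, and the trial continues. The size of any bias cannot be derived from the documents.

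Timing is uncertain. SAP 6.2.4 and 6.2.5 define populations of interim participants, SAP 9 attributes them to a pre-NDA meeting, and SAP 6.11.5 already refers to few participants with pain. These suggest that the interim may have passed before this SAP version, although SAP 8 uses the future tense. Nothing shows which of the two rules was followed.

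**What to change.** Amend Protocol 16.4 so that the Executive Committee receives only pooled enrolment, retention and safety data and the DSMB's recommendation. State that between-arm interim results, and any DSMB report that is unmasked or presented by arm, go only to the recipients allowed in SAP 7. NIDCR has representatives on the committee and is also consulted about stopping (Protocol 12.3.1), so say on which side of the firewall those representatives sit.

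The cost is a sentence or two in an amendment. No stated decision role is lost: Protocol 12.3.1 names the DSMB, NIDCR and the IRBs as those consulted on stopping, not the committee.

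If the interim has already taken place, an amendment alone protects nothing. The clinical study report should then document who received which interim results, in what form (pooled, coded or unmasked) and on what date.
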